**Visit Window Periods**

For each study participant, the window period for conducting a study visit is as follows:

- Cohort A: +/- 3 days for all study visits before and including two months, and +/- 7 days for all visits afterwards
- Cohort B & C: +/- 14 days

**TABLE 1: SCHEDULE OF EVALUATIONS FOR ACTIVE TB COHORT**

CRF   Time	Entry	2W	4W	8W	5M	6M	12M	18M	24M	End of Tx	TB recurrence (failure, relapse)
Consent/Enrollment	X										
Medical History	X										
Psychosocial Interview	X			X		X	X	X		X	X
Socio-demographic Interview	X										
Clinical Assessment (i.e. TB and Lung Health Assessment, Physical examination  , Concomitant Meds, Diagnoses/AEs)/ Medication History	X	X	X	X	X	X	X	X	X	X	X
TB Medication Adherence	X	X	X	X	X	X				X	
Nutrition Assessment 	X					X				X	X
Anthropometrics 	X	X	X	X	X	X	X	X	X	X	X
Chest Radiograph 	X			X		X					X
Sputum AFB and culture X 2 (DST if culture+) 	X	X	X	X	X	X		X		X	X
Sputum for Cepheid Gene-Xpert X 2	X										X
Extrapulmonary TB sample for AFB and culture/histopathology	X 										X
Hematology (CBC)	X			X							X
HIV Test (if not already known)	X										X
CD4 count if HIV +ve 	X										X
Hemoglobin A1c (Adults) 	X									X	X
LFT	X		X	X						X	X
Chemistry (Renal panel, glucose)	X									X	X
Urinalysis	X										X
Urine Pregnancy test	X			X		X					X
PFT (Adults), Spirometry (Child) (random subset)				X						X	X
Samples for Biorepository	Entry	2W	4W	8W	5M	6M	12M	18M	24M	End of Tx	TB Recurrence
Stored Plasma sample for PK 			X		X						
Stored Plasma	X		X	X		X	X		X	X	X
Whole Blood for DNA				(X) 							
Stored Sputum	X	X	X	X		X				X	X
Stored Urine	X		X	X		X	X		X	X	X

Stored Hair	X		X		X	X				X	X
Stored Mtb isolate	X			X	X	X					X
Whole Blood for Host mRNA (PAXgene)	X		X	X		X	X		X	X	X
Whole Blood forPBMC	X		X	X		X	X		X	X	X
Whole blood for Quantiferon supernatant	X		X	X		X	X		X	X	X

 Active TB participants with Microbiological Confirmation of TB (defined as smear+, Xpert+, or smear negative but cultured confirmed. Patients who are initially negative by smear and/or Xpert will be enrolled if they meet criteria for Cat-1 TB treatment. Participants who remain culture negative by 3 months will be follow-up but will not be included in the primary analysis.

 An additional 'End of Rx' time-point to be observed for participants with Rx duration exceeding 6 months

 Indoor Air Pollution monitoring will be done only on a subset of cohort B households.

 Household food insecurity

 A complete physical exam at entry. At post-entry visits, a targeted physical exam will be performed

 For adults and children: Height / length, mid upper arm circumference, weight at baseline. At post entry visits, weight and height / length will be measured

 A 2 hour post TB drug dose (participant will take their dose in clinic and will have the time noted for a blood drawn 2 hours post dose administration)

 Additional EPTB samples to be collected at the discretion of the onsite clinical staff. These specimens are collected as part of clinical evaluation only and will not be retained/repeated for study purposes.

 CXR at baseline will be done unless one was taken as a part of the clinical investigation of the participant's TB through the RNTCP. Data from an 8 week and 6 month CXR will be collected if testing was done as part of the RNTCP standard of care or if participant has pulmonary disease. Pregnant women are not required to have CXR. CXR will be done at End of Tx if it didn't overlap with 6M

 CD4 count will only be performed on participants who have not had a CD4 count tested in the preceding 6 months.

 End of Treatment assessment of HbA1c will be selectively done on those participants with abnormal HbA1c at baseline

 Can be collected at any time-point between 2W and 6M

 At enrollment, one spot specimen and one early morning specimen will be obtained from all Cohort A participants. Diagnostic tests will be run on both specimens. During subsequent visits, two sputum spot specimens will be collected, and will be pooled for testing. The remaining specimens would be stored.

**TABLE 2. SCHEDULE OF EVALUATIONS FOR HH CONTACTS COHORT**

Time	Entry	4M	6M	12M	18M	24M	Active TB 
Consent/Enrollment	H						
Medical History	H						
Brief Psychosocial Interview	H			H		H	F
Brief Socio-demographic Interview	H						
Clinical Assessment  (i.e. TB and Lung Health Assessment, Concomitant Meds)/Medication History	H	H	H	H	H	H	F
Urine Pregnancy test	H	(H)					F
Nutrition Assessment 	H	H	H	H	H	H	F
IAP	H	H	H				
Targeted Physical Exam and Anthropometrics 	H	H	H	H	H	H	F
Chest radiograph	F	(F)					F
Sputum AFB and culture x 2 (DST if culture +)	H	H					F
TT Skin Test	H	H 		H 		H 	
Quantiferon Gold in Tube	H	H 		H 		H 	F
CBC	H						
Rapid HIV Test 	H						F
Hemoglobin A1c Point of care (Adults)	H			H			F
Household Air Sample (random subset)	H	H		H			
PFT (Adults), Spirometry (Child) (random subset)	H			H			
Samples for Biorepository							
Stored Plasma	H	H		H			F
Stored DNA	H						
Stored Sputum	H	H					F
Stored Urine	H	H		H			F
Stored Hair	H	H		H			F
Stored MTB isolate	H						F
Stored QGIT supernatant	H	H		H		H	F
Stored Host mRNA (Paxgene)	H	H 		H 			F
Stored PBMC	H	H 		H 			F

**F=Facilities-based activity; (F)= Facility Based activity only if indicated; H= Home-based activity; M=months**

 Any person who has active TB (prevalent or incident) is eligible for the Active TB Cohort if he or she consents. Active TB assessment will otherwise be done as included in this SOE if the participant does not enroll in the Active Cohort.

 All symptomatic household contacts will be referred immediately to the clinical facility for further evaluation. IPT will be recommended for all asymptomatic children under age 6 and all asymptomatic HIV+ household contacts

 Household food insecurity and dietary questionnaire

 Height, mid upper arm circumference, weight at baseline; at post entry visits, weight will be measured

 TST and QGIT will only be done if prior was negative

 HIV testing will only be done on adults. If there is a HIV+ adult in the household, then the legal guardian of the child will be asked if they want their child to be HIV tested

 Host mRNA, PBMC, saliva, will be performed on all at baseline and then a random subset of 200 households (n=800 contacts)

**TABLE 3 . SCHEDULE OF EVALUATIONS FOR CONTROL HOUSEHOLDS COHORT**

Time	Entry	4M	12M
Consent/Enrollment	H		
Medical History	H	H	H
Brief Psychosocial Interview	H		H
Brief Socio-demographic Interview	H		
Clinical Assessment  (i.e. TB Assessment, Concomitant Meds)/ Medication History	H	H	H
Nutrition Assessment 	H	H	H
Urine Pregnancy Test	H		
Targeted Physical Exam and Anthropometrics 	H	H	H
TT Skin Test	H	H 	H 
QGIT	H	H 	H 
CBC	H		
Rapid HIV Test 	H		
Hemoglobin A1c Point of Care (Adult)	H		
IAP & HH Air Sample (random subset)	H		
Samples for Biorepository			
Stored Plasma	H	H	H
Stored DNA	H		
Stored Sputum	H	H	H
Stored Urine	H	H	H
Stored Hair	H	H	H
Stored Stimulated QGIT	H	H	H
Stored Host mRNA (PAX gene)	H	H 	H 
Stored PBMC	H	H 	H 

**H= Home-based activity; M=months**

 Controls have to be without evidence of TB or acute illness to be eligible at entry. If during follow-up, any control is noted to have clinically concerning symptoms (e.g. fever, cough, diarrhea) then sample will not be collected and they will be referred for further care.

 Household food insecurity and dietary questionnaire

 Height, mid upper arm circumference, weight at baseline; at post entry visits, weight will be measured

 TST and QGIT will only be done if prior was negative

 HIV testing will only be done on adults. If there is a HIV+ adult in the household, then the legal guardian of the child will be asked if they want their child to be HIV tested

 These additional samples will be taken at baseline from all and a random sample of 20 households (100 people) at time points shown in green

### 6.3. LABORATORY EVALUATIONS

Sputum studies: Two sputum specimens (approximately 5 ml each/visit) will be collected at baseline, one spot and one early morning will be collected from adult active TB cases and HH contacts and will be processed for AFB smear and liquid media cultures (MGIT). On active TB cases only, Cepheid Gene Xpert MTB RIF will also be done. A drug sensitivity test (DST) will be performed if culture is positive.

For participants in the Active TB Cohort, samples will be taken at baseline (BL), 2, 4, 8 weeks (W), 5 months, 6 months (M), end of treatment and at recurrence. For all visits after enrollment two spot/early morning specimens will be collected one for testing and one for storage.

For household contacts: BL and 4M for Processing and storage

For Control Cohorts : BL, 4M & 12M for storage

For children < 5 years who are active TB cases, two gastric aspirates will be collected and will be processed for smear, rapid TB identification by Xpert MTB RIF assay and MGIT. For children in contact and control HHs, if a TB symptom screen is positive then they will be referred to the clinic to have sputum of gastric washing studies done as age-appropriate.

EPTB samples: Additional smear and cultures and histopathology of extra pulmonary specimens will be performed as clinically indicated.

Urine samples: Up to 10 ml will be taken at each visit. For participants in the Active TB Cohort, samples will be taken at BL, 4 and 8W, 6M, end of treatment, at recurrence and an additional sample will be taken at BL for urinalysis. For household contacts and controls, samples will be taken at BL and 4 and 12 months for storage purposes. Dipstick urinalysis will be performed with microscopic examination as necessary.

Females of reproductive potential (girls who have reached menarche, women who have not been post-menopausal for at least 24 consecutive months, (i.e., who have had menses within the preceding 24 month), or women who have not undergone surgical sterilization, hysterectomy or bilateral salpingectomy or bilateral oophorectomy or tubal ligation) must receive urine pregnancy test at the time of enrollment and a card pregnancy test will be performed before chest xrays taken.

Chest radiograph: CXR will be performed at baseline unless one was taken as a part of the clinical investigation of the participant's TB through the RNTCP. Data from an 8 week and 6 month CXR will be collected if testing was done as part of the RNTCP standard of care or if participant has pulmonary disease.

Pulmonary Function Tests/ Spirometry: Diagnosis of asthma/COPD will be performed on a random subset using portable PFTs (adults) and spirometry (children >5 years) to corroborate self-report as well as measure post-treatment lung health in Active TB Cohort and risk of development of TB in Contact Cohort.

Blood samples: Blood samples will be collected for storage and safety laboratory tests. Maximum of up to 28ml of blood will be taken from a vein for adults (age group >14 years) during study visits. Up to 20ml will be stored for future tests while remaining will be used for safety tests and CD4 counts. For children, the total volume of blood being collected shall not exceed 3ml/kg body weight in an 8 week period.

For storage -

For participants in the Active TB Cohort, samples will be taken at BL, 4 and 8W, 5M, 6M, 12 month, 24 months, end of treatment, and at recurrence.

For household contacts and controls, samples will be taken at BL and 4, 12 and 24 months.

For control cohort, samples will be taken at BL and 4, 12months.

For safety labs – following tests will be performed -

- a) Hematology: Complete Blood Count (CBC) with differential will be obtained for both all 3 cohort participants.
- b) HIV Studies: If HIV status is unknown, HIV testing will be performed on consenting adult participants. Children less than 18 years will only be tested for HIV if they are active TB cases or if a parent has tested positive or is known to be HIV-infected.
- c) Hemoglobin A1c for DM: Hemoglobin A1C, a recommended test for DM will be done for all adult participants of all three cohorts.
- d) Chemistry: Renal panel: Blood urea nitrogen (BUN), creatinine;  
*Liver Function Tests (LFTs):* Total bilirubin, AST, ALT, alkaline phosphatase and glucose.

Tuberculin Skin test (TST): A TST skin test will be placed and read ideally 48-72 hours (but within 1 week is acceptable) of placement on all HH contacts and controls. It will only be performed at follow-up visits if prior results were negative.

Quantiferon Gold in Tube (QGIT): Approximately 3 mLs of blood will be collected and processed for QGIT in Active TB cohort participants at BL, , 4W, 8W, 6M, 12M, 24M, end of treatment and at recurrence; in HH cohort participants at BL, 4M, 12M, 24M, TB activation and in control cohort participants at BL, 4M and 12M.

HH Exposure to IAP: HH samples will be collected on a random subset to estimate air particle concentration (PM 2.5) and carbon monoxide as an objective marker for exposure to IAP from biomass fuels and corroborated with IAP questionnaire data.

Sample of hair: A small thatch of hair (~30-50 strands) will be collected for the hair sample.

For Active TB Cohort hair sample will be taken at BL, 4W, 5M, 6months, End of Tx and Recurrence;

For household contacts and controls: BL and 4 and 12 months.

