**TABLE 4: BIOSTORAGE STUDY SPECIMEN COLLECTION AND STORAGE CHART (ADULTS AND CHILDREN)**

Specimens Type	Adults and Children ( years)	Children (< 5 years) a
Whole blood (PAXgene tubes)	2.5 mL	2.5 mL b
Whole blood (QuantIFERON-Gold InTube)	3.0 mL (1.0 mL/tube)	3.0 mL (1.0 mL/tube)
Whole blood (Genotyping)	10 mL	DO NOT COLLECT IF VOLUME EXCEEDS REGULATORY LIMITS
PBMCs	8.0 mL (BD CPT™)	4.0 mL (BD CPT™)
Plasma	Harvested from BD CPT™ (PBMC) tubes above	Harvested from BD CPT™ (PBMC) tubes above
Urine	Spot urine (10 mL)	Spot urine (10 mL)
Sputum	Whatever volume is possible to collect	Whatever volume is possible to collect
Extracted host RNA	Prepared from PAXgene tube	Prepared from PAXgene tube
M.Tb isolate	Cohort A	Subculture of original Mtb isolate and relapse or failure isolate.
	Cohort B	Subculture of confirmatory Mtb isolate from each subject who develops active TB

a Refer to weight chart for maximum blood volume collection limits in MOP. Indicated blood collection volumes are intended for children ≥ 5 kg (or 11 lbs) .

bExclude from collection if combined study and biobank blood volume limit is exceeded –Maximum combined blood volume collection is limited 2.5 mL/kg.

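### Two unreconciled blood-volume limits for children, and an Active TB Cohort schedule whose cumulated under-5 volumes exceed the 8-week limit in the lightest children

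*Protocol*

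**What the plan says.** Section 6.3 (Blood samples) gives the first limit: "For children, the total volume of blood being collected shall not exceed 3ml/kg body weight in an 8 week period". It covers total blood and has an 8-week base.

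Table 4 in section 7.1 gives the second. Its footnote b is marked on the PAXgene entry for children under 5 years. It reads "Exclude from collection if combined study and biobank blood volume limit is exceeded" and then "Maximum combined blood volume collection is limited 2.5 mL/kg". No period is attached.

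Three further statements in Table 4 bear on the point:

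- Footnote a, placed on the header of the under-5 column, says "Refer to weight chart for maximum blood volume collection limits in MOP". It continues, "Indicated blood collection volumes are intended for children" of 5 kg or more.
- The genotyping row for under-5s carries its own stop: "DO NOT COLLECT IF VOLUME EXCEEDS REGULATORY LIMITS".
- The QuantiFERON (QGIT) and PBMC rows carry no withholding note of their own.

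The under-5 volumes are 2.5 mL for PAXgene, 3.0 mL for QGIT and 4.0 mL for PBMC. Plasma comes from the PBMC tube.

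Table 1 (Schedule of Evaluations for Active TB Cohort) marks PAXgene, PBMC and QGIT at Entry, 4W and 8W, with no exception for children. Section 6.3 repeats those time points for storage blood and QGIT. Section 5.3 excludes children below 5 kg from all three cohorts.

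**The concern.** Both sentences govern a child's total blood, yet they give different figures and only one has a time base. A site working from one passage alone could breach the other. Separately, the sampling schedule and the volumes table appear to have been written without adding them up against the 8-week limit.

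This is a safety limit in a study that plans to enrol 200 children with TB and accepts children from 5 kg. Table 4 presents its volumes as suitable from that weight. If the limit, the volumes and the schedule cannot all be followed as written, sites and ethics committees do not have a clear rule. The primary analysis for Aim 1 is in adults with pulmonary TB, so the issue is participant protection and internal consistency, not inference.

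**Working it through.** The protocol states no cumulative volume for children, so there is no plan figure to reproduce. The check is arithmetic on its inputs.

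**Inputs.** Limits: 3 mL/kg in 8 weeks (section 6.3) and 2.5 mL/kg with no period (Table 4, footnote b). Under-5 volumes: 2.5, 3.0 and 4.0 mL (Table 4). Draws: Entry, 4W and 8W (Table 1, Active TB Cohort). Lowest eligible weight: 5 kg (section 5.3). Genotyping blood is counted as zero because the table makes it conditional.

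**Step 1: the limits at 5 kg.** 3 × 5 = 15.0 mL and 2.5 × 5 = 12.5 mL.

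**Step 2: one collection.** 2.5 + 3.0 + 4.0 = 9.5 mL; 9.5 / 5 = 1.9 mL/kg. Without PAXgene, 3.0 + 4.0 = 7.0 mL. A single collection is below both limits for every eligible child.

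**Step 3: cumulated over the draws in 8 weeks.** Total = volume per collection × number of draws. The section 6.3 limit is exceeded when weight is below total / 3.

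| Draws in 8 weeks | Samples | Total (mL) | mL/kg at 5 kg | Section 6.3 limit exceeded below |
|---|---|---|---|---|
| 1 | all three | 9.5 | 1.9 | 3.17 kg (no eligible child) |
| 2 | all three | 19.0 | 3.8 | 6.33 kg |
| 3 | all three | 28.5 | 5.7 | 9.5 kg |
| 2 | without PAXgene | 14.0 | 2.8 | 4.67 kg (no eligible child) |
| 3 | without PAXgene | 21.0 | 4.2 | 7.0 kg |

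**Step 4: can three draws fall in one 8-week period?** Yes. Section 6.1 times visits from the start of TB treatment, section 5.3 tolerates up to a week of prior therapy at enrolment, and the window at 8W is ±3 days. The Entry-to-8W interval can therefore be 8 weeks or less. It can also be slightly more, in which case two draws count.

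**Step 5: room for other blood.** With two draws and PAXgene withheld, a 5 kg child has 15 − 14 = 1 mL left under section 6.3. Table 1 also schedules LFT at Entry and 4W, CBC, chemistry and, where status is unknown, an HIV test at Entry, and a PK sample at 4W. The protocol gives no child volumes for these, so every total above is a lower bound.

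**Step 6: the two limits against each other.** Footnote b can be read in two ways, which are alternatives:

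- *Over the same 8 weeks.* A child bled between 2.5 and 3 mL/kg meets section 6.3 and breaches footnote b. At 5 kg that is between 12.5 and 15 mL, and the 14 mL case falls there. On this reading the three-draw totals exceed footnote b below 28.5 / 2.5 = 11.4 kg, or 21 / 2.5 = 8.4 kg without PAXgene.
- *Per visit.* The listed volumes satisfy footnote b at every eligible weight, before safety and PK blood. Three visits at that ceiling would total 3 × 2.5 = 7.5 mL/kg, which section 6.3 forbids.

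**Step 7: other cohorts.** Contacts and controls have storage draws at Entry and 4M, so one per 8 weeks. For under-5s that is 1.9 mL/kg at 5 kg, below both limits on storage blood alone.

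**The case against.** The strongest reply is that section 6.3 is mandatory and overrides the schedule, so a site would withhold tubes and not exceed it. Both limits can be met at once by staying under whichever is tighter. Footnote a covers the whole under-5 column and sends sites to a weight chart in the Manual of Operation. Section 7.1 leaves collection details to that manual, and section 13 promises age-appropriate volumes in line with international guidelines. Much of this stands. The manual is not available here, and it may already restrict every tube. What it cannot do is make two different figures in the protocol agree or supply footnote b's missing time base within the protocol.

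Four stronger readings are tempting but not supported:

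- *Table 4's volumes themselves exceed both limits.* They do not: one collection is below both. The excess needs the Active TB Cohort schedule.
- *The protocol permits 7.5 mL/kg in 8 weeks.* It does not, because section 6.3 still binds. That figure also needs the per-visit reading, while the 8.4 and 11.4 kg thresholds need the 8-week reading, so they cannot be used together.
- *All the smallest children in the study are affected.* On storage blood, under-5 contacts and controls are not.
- *Sites will drop different tubes, leaving repository data missing by site and weight.* Without the manual this is conjecture.

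It is also fair that the excess after withholding PAXgene depends on counting three draws. With two, 14 mL is within the section 6.3 limit at 5 kg, before safety and PK blood.

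**Conclusion.** The point holds in a limited form. The protocol contains two blood-volume limits for children, 3 mL/kg in 8 weeks and 2.5 mL/kg with no period, and does not relate them. The under-5 volumes taken on the Active TB Cohort schedule do not fit the 8-week limit in the lightest children. They come to 28.5 mL against 15 mL allowed at 5 kg (excess below 9.5 kg), or 21 mL with PAXgene and genotyping withheld (excess below 7.0 kg).

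These sizes assume three draws within one 8-week period, zero genotyping blood, and no further withholding under the manual's chart. They leave out safety and PK blood, which would raise them. The number of enrolled children in these weight ranges cannot be derived from the protocol. The issue is safety-relevant and cheap to correct, and it does not touch a primary outcome analysis.

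**What to change.** Reconcile section 6.3, Table 4 with its footnotes, the Active TB Cohort schedule in Table 1 and the manual's weight chart. The protocol should then state one limit, with one explicit time base, covering study and biobank blood together. Cumulate the Table 4 volumes, plus safety and PK blood, over the Active TB Cohort draws in that period and check them against the limit by weight. Make the schedule and the table's exclusion notes consistent with the result. Which limit applies, and which samples are withheld, is for the clinical and ethics leads.

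The cost is a wording amendment and alignment with the manual. Some repository aliquots may be lost in the lightest Active TB Cohort children.

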## 7. PROPOSED SPECIMEN REPOSITORY

This section will describe the purpose and specific details for collecting blood, urine, and sputum specimens from participants in each of the three cohorts (active TB cohort, HH contact cohort and control cohort) for placement in biostorage for future studies. The samples will be curated, stored, and managed at the Central Repository - National Institute for Research in Tuberculosis, Chennai. All participants will be consented for long term storage of samples. The resultant “bank” of biological samples will be made available to investigators participating in the RePORT-India Consortium through a peer-review process that considers high-priority, credible proposals for their use. Example purposes for stored specimens (reference Am J Respir Crit Care Med 184: 972-979, 2011) include but are not limited to:

- **M. Tb isolates** for full genome sequencing for virulence factors, association with clinical outcomes, and in the case of relapse, for comparison to the baseline specimen.
- **Plasma** for proteomics, metabolomics, lipidomics, and noncellular measures of immune response (i.e., cytokines, chemokines).
- **Whole blood** for transcriptomics.
- **Whole blood stimulated with mycobacterial antigens** yielding supernatant to be stored for measuring non-cellular immune responses, e.g., chemokines, cytokines.
- **Peripheral blood mononuclear cells (PBMCs)** to measure CD4, CD8 and other cellular immune responses.
- **Urine** for metabolomics and measures of microbial markers.
- **Sputum** for mRNA, microbiologic measures and host immune markers.

While this valuable resource will be primarily for use within India, it is expected that the “bank” will also be available to investigators external to the Consortium if they propose to work together with a Consortium member or group of sites and assuming that the appropriate ethical and scientific approvals are obtained.

Since this study requires collection of additional samples and testing beyond what is normally collected or tested for participants being treated in the Revised National TB Control program, ethics committee approvals will be required. Because of the rapidly developing science in this field, it is not possible to predict precisely what tests will be performed with these samples. In addition, many important discoveries are likely to be made through the analysis of human DNA and RNA and thus informed consent for this use will also be sought, which will include subsequent testing for genetic markers.

